Study Protocol and Statistical Analysis Plan for NCT03750968

Lutein & Zeaxanthin in Pregnancy – Carotenoid Supplementation during Pregnancy: Ocular and Systemic Effects

The following pages contain the IRB approved study protocol and statistical analysis plan at the most recent renewal approved on 21 December 2022.

Date: Tuesday, May 2, 2023 2:01:03 PM

[Print](#)
[Close](#)
IRB_00116610
Created: 10/1/2018 12:13 PM

IRB_00116610

1. Contacts and Title

PI: [name]

Submitted: 11/21/2018

Title: Lutein & Zeaxanthin in Pregnancy (L-ZIP) - Carotenoid Supplementation During Pregnancy: Ocular and Systemic Effects

1. Study Introduction

1. Responsible Investigator:

[name]

Email	Training	Col Date
[contact]	7/27/2021 MCG	4/3/2023

a. Position of the Investigator:

- Faculty or Non-Academic Equivalent
- Student
- Staff
- Resident/Fellow
- Other

2. Contact Persons for the Responsible Investigator:

Name	Email	Training
[name]	[contact]	1/30/2023 MCG
[name]	[contact]	CG
[name]	[contact]	1/31/2023 MCG
[name]	[contact]	1/4/2023 MCG
[name]	[contact]	6/17/2022 MCG

3. Guests of the Responsible Investigator:

Last Name	First Name	E-Mail
-----------	------------	--------

There are no items to display

4. What type of application is being submitted?

[New Study Application](#) (or Amendment/Continuing Review)

5. Title Of Study:

Lutein & Zeaxanthin in Pregnancy (L-ZIP) - Carotenoid Supplementation During Pregnancy: Ocular and Systemic Effects

6. Study Purposes and Objectives:

The primary objective of this study is to characterize the carotenoid status of mothers during pregnancy, specifically to determine if prenatal supplementation counteracts maternal systemic and ocular carotenoid depletion.

The primary outcome measure will be change in carotenoid levels from enrollment to final study visit (birth of child) as measured in serum, skin and the macula by high-performance liquid chromatography (HPLC), resonance Raman spectroscopy, and macular pigment imaging, respectively.

7. Is this a multi-site study, where more than one site needs IRB approval?

Yes No

8. Background and Introduction:

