Initial evaluation of each mother's carotenoid status will be obtained prior to starting any study supplements. Subsequent evaluations while participants are taking the study supplements will be performed in conjunction with routine prenatal visits to their Obstetrician, at approximately 22-26 weeks gestational age and again at 37-39 weeks gestational age. All mothers will undergo a final assessment within two weeks of giving birth.

Infants' evaluations will be performed in the first two weeks of life, either during the original hospital stay or at a follow up outpatient clinic visit.

Visit:	Screening/ Baseline	Maternal Supplementation		
	T1	T2	T3	Birth
Timeframe:	Before 14 Wks GA	22-26 Wks GA	37-39 Wks GA	0 to 2 Wks
Informed Consent	X			
Randomization	X			
Maternal visual acuity and contrast sensitivity	X	X	X	X
Maternal nutritional surveys	X	X	X	X
Dilated eye examination	X			
Maternal serum carotenoids	X	X	X	X
Maternal macular pigment imaging	X	X	X	X
Maternal skin carotenoids	X	X	X	X
Dispense prenatal supplement and do pill counts	X	X	X	X
Infant cord blood carotenoids				X
Infant macular pigment imaging				X
Infant foveal imaging (sdOCT)				X
Infant skin carotenoids				X

Unscheduled Visits

Mothers may be seen for Unscheduled Visits if deemed necessary for repeat measurements or follow-up of Adverse Events. If a mother delivers her baby prematurely, she and her infant will remain in the study and will be asked to complete the final study visit.

Description of Study Assessments:

Visual Function - Manifest refraction, and measurement of best-corrected visual acuity and contrast sensitivity of the mothers will be obtained by certified ophthalmic technicians using standardized protocols. The study staff performing visual acuity will be masked to the treatment assignment. Best-corrected visual acuity testing will be assessed on ETDRS back-lit charts starting at a distance of 4 m, and should precede any examination requiring administration of eye drops to dilate the eye or any examination requiring contact with the eye. Contrast sensitivity will be measured by the Pelli-Robson threshold contrast sensitivity chart at 1 m.

Maternal Eye Exam - The complete ophthalmic exam will consist of the following:

- External examination of the eye and adnexa.
- Routine screening for eyelids/pupil responsiveness (including ptosis, abnormal pupil shape, unequal pupils, abnormal reaction to light and afferent pupillary defect).

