Maternal Macular Pigment Levels - Mothers' macular pigment will be measured using the dual wavelength autofluorescence method which measures attenuation of lipofuscin autofluorescence by blue absorbing macular pigment. The subject looks at a fixation target with her dilated study eye for about 30 seconds as her macula is scanned sequentially with alternating 486 nm (blue) and 518 nm (green) lasers, and autofluorescence images are collected. Macular pigment images are prepared by digitally subtracting the green image from the blue image using appropriate correction factors to compensate for the absorption spectrum of the macular carotenoid pigment and then analyzed using macular pigment analysis software after setting the zero point at 9 degrees of eccentricity. This instrument and software has proven to be highly reliable and reproducible, especially when measuring macular pigment volume under the curve at 9 degrees.

Serum Carotenoid Levels - Blood samples obtained from mothers and from infant cord blood will be analyzed for serum carotenoid content using well-established laboratory protocols that can provide baseline separations of all common dietary carotenoids. Whenever possible blood samples will be obtained by piggy backing onto a routine clinical blood collection.

Dietary Questionnaires - At each study visit mothers will be asked to complete the LZQ quantitative food frequency questionnaire that captures ~90% of the lutein/zeaxanthin foods consumed in the US, based on National Health and Nutrition Examination Survey data.

Safety Evaluations - Any clinically significant abnormalities persisting at the end of the study/ early withdrawal will be followed by the investigator until resolution or until a clinically stable endpoint is reached. The study includes procedures to monitor safety, including complete Ophthalmic exams and monitoring of adverse events.

Optional Specimen Collection and Banking Sub-Study

Participants will be asked to allow a sample of placenta tissue to be collected and stored for future research related to maternal to infant carotenoid transport on a tissue level.

Participants will be asked to provide a saliva sample to be stored and used for future research related to the genetics of carotenoid metabolism enzymes.

Participants will be asked to allow a portion of their blood collected at study visits to be stored for future research related to the genetics of carotenoid metabolism.

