Statistical power and sample size (N) for one of the primary outcome measures, maternal skin carotenoids at birth, was determined using data from the previous study by Henriksen et al. (2013) in which the average maternal skin carotenoids \pm SD at birth was 34000 ± 8300 . This value is 20% lower than the University of Utah Moran Eye Center clinic average value of $\sim 42,500$ Raman counts reported for the ancillary AREDS2 study ([name] et al., 2012). With power of 0.90 and alpha 0.05, a sample size of 20 was calculated for each group in order to detect and prevent a 20% decline during pregnancy. In order to accommodate subsequent ineligibility due to premature birth, low birth weight, or other problems ($\sim 10\%$) and to plan for expected noncompliance and loss to follow up ($\sim 20\%$), we intend to enroll 30 subjects in the Carotenoid Supplementation Group and another 30 in the Control Group.

The other outcome measures (maternal ocular carotenoid depletion during pregnancy, infant carotenoid status at birth, and the exploratory outcome measures of foveal maturity at birth and visual function changes during pregnancy) are not as well characterized, but we estimate that a similar sample size of 20 patients per group will be sufficient to detect differences in these indices.

Statistical Analysis Sets

The Intent-to-Treat set will include all randomized subjects who complete the Baseline Visit carotenoid status evaluations and receive study supplements. Subjects will be analyzed by the supplement arm assigned at the Baseline Visit.

A modified Intent-to-Treat set will include all randomized subjects who receive investigational product and complete carotenoid evaluations for at least one trimester study visit while utilizing study supplements.

Efficacy Analyses

The primary, secondary and exploratory efficacy analyses will be performed using the modified Intent-to-Treat subject set. Paired t-tests will compare the carotenoid status at enrollment and at the final study visit of the mothers receiving carotenoid supplementation to mothers not receiving carotenoid supplementation. We will also compare carotenoid status of infants whose mothers received carotenoid supplementation to infants of mothers without carotenoid supplementation. Significance will be set at 2-tailed $P < 0.05$. The associations between maternal and infant carotenoid status will be assessed with regression analysis.

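### The efficacy set admits women with no birth-visit value, but the only stated maternal test needs one, so women who leave after T2 or T3 drop out by default and their data go unused

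*Combined protocol and SAP*

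**What the plan says.** Section 1, item 6 (Study Purposes and Objectives) defines the primary outcome as "change in carotenoid levels from enrollment to final study visit (birth of child", measured in serum, skin and macula. The final visit is thus tied to delivery.

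Section 4, item 6 (Study Visit Schedule) measures maternal serum, skin and macular carotenoids at baseline, "at approximately 22-26 weeks gestational age and again at 37-39 weeks gestational age" (T2 and T3), and at a separate visit within two weeks after birth. Women who deliver prematurely stay in the study and are asked to attend that visit. Nothing equivalent is said about women who stop the softgels.

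Section 4, item 9 supplies the analysis:

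- Efficacy Analyses: "The primary, secondary and exploratory efficacy analyses will be performed using the modified Intent-to-Treat subject set".
- Statistical Analysis Sets: to enter that set, a randomized woman must receive product and "complete carotenoid evaluations for at least one trimester study visit while utilizing study supplements". T2 alone is enough.
- Efficacy Analyses: "Paired t-tests will compare the carotenoid status at enrollment and at the final study visit of the mothers", for supplemented against unsupplemented mothers.
- Sample Size Calculation: about 20% is added "to plan for expected noncompliance and loss to follow up", and about 10% for later ineligibility. Enrolment is 30 per arm against 20 evaluable.
- The end of the efficacy text says that a complete analysis plan, to be finalized before database lock, will describe how missing data are handled. It names no method.

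**The concern.** The analysis set and the test do not fit each other. The set is built to keep women with partial follow-up; the test can use only women with both an enrollment and a birth value. Unless something else is specified, the population analysed is smaller than the population declared, and it is selected by who stayed to the end.

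Two things are at stake. If staying is related to how a woman's carotenoid levels are moving, the comparison among those who remain can be biased. And two rounds of measurements in three tissues, already scheduled for every mother, have no role in the stated maternal efficacy analysis, although they carry information about the missing birth values.

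**Working it through.** **1. The mismatch.** Entry to the set needs one evaluated visit at T2 or T3. Entry to the test needs enrollment and Birth. Final visit cannot mean last available visit, because Section 1 ties it to birth and the schedule lists Birth after T3. A woman seen at T2, or at T2 and T3, and then lost is in the set and outside the test. This holds whether the paired test is read as a within-arm test or as a comparison of changes, since both need the two values.

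**2. The plan's sample size.** Inputs from item 9: SD 8,300; difference 42,500 − 34,000 = 8,500; two-sided alpha 0.05; power 0.90.

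n per arm = 2 × [8,300 × (1.960 + 1.282) / 8,500]² = 20.04.

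The stated 20 reproduces (normal-approximation power 0.899 at n = 20).

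**3. How many women.** 20% of 30 = 6 per arm. This is an upper bound: the 20% also counts noncompliance, noncompliant women may still attend Birth, and women lost before T2 are outside the set anyway. Completers are then 30 − 6 = 24 per arm, or 30 × 0.70 = 21 if the 10% ineligibility is also removed. Power on the plan's own basis (normal approximation) is 0.944 at 24 and 0.913 at 21; t-based, 0.935 and 0.899.

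**4. Bias (illustration).** The documents give no between-visit correlation and no dropout mechanism, so these are assumed. Simulation: 400,000 women per arm; four visits; SD 8,300; equal correlation between visits; controls fall from 42,500 to 34,000; supplemented women stay at 42,500; 20% of the supplemented arm leave after T3, with log-odds of leaving up by 1 per SD lower T3 change; no control loss.

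| Correlation | Completers' difference | Excess over 8,500 | SE of difference in change, 24 vs 30 women | Excess / SE |
|---|---|---|---|---|
| 0.6 | 9,137 | 637 (7.5%) | 2,033 | 0.31 |
| 0.7 | 9,057 | 557 (6.6%) | 1,761 | 0.32 |
| 0.8 | 8,954 | 454 (5.3%) | 1,438 | 0.32 |

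SE = 8,300 × √[2(1 − ρ)] × √(1/24 + 1/30). Repeat runs agreed within about 12 counts. At 5% loss the excess is about 110–170 counts. Using baseline, T2 and T3 returns about 8,500, as it must here, because leaving was made to depend only on observed values.

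Other assumed patterns, with leaving after T2 likelier when the T1–T2 change is low (correlation 0.3 to 0.8):

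- 30% control and 10% supplement loss: the difference is 7,503 to 7,970, or 6–12% too small.
- 20% loss in each arm: the difference is unbiased, but the control arm's own decline reads about 7,370 to 7,900 instead of 8,500. That matters if the paired test is read within arm.
- Loss completely at random: no bias.

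**5. Precision gained by using T2 and T3.** Take 24 completers and 6 leavers per arm, loss at random, equal correlation ρ, variances in units of SD².

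- Baseline-adjusted completers: V_c = (1 − ρ²)/24.
- Repeated-measures model: V_m = r/24 + (1 − ρ² − r)/30, where r is the variance of Birth given all earlier observed visits: 1 − 3ρ²/(1 + 2ρ) if the six leave after T3, and 1 − 2ρ²/(1 + ρ) if they leave after T2.

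| ρ | Leave after | V_c | V_m | √(V_c/V_m) |
|---|---|---|---|---|
| 0.6 | T3 | 0.02667 | 0.02558 | 1.021 |
| 0.8 | T3 | 0.01500 | 0.01418 | 1.028 |
| 0.6 | T2 | 0.02667 | 0.02592 | 1.014 |
| 0.8 | T2 | 0.01500 | 0.01441 | 1.020 |

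The completers' interval is about 1.4–3% wider than the model's.

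**The case against.** The strongest reply is that item 9 is only a summary. It promises a complete plan before database lock that will cover both methods and missing data, and it states no rule for discarding anyone. A reader might infer that the sponsor has chosen a completers-only analysis; the documents do not say so. That part of the reply stands. It does not remove the point, because the deferral names no method while the one test that is named cannot use these women.

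The size can also be challenged, and much of that stands. Loss after T2 or T3 is not quantified. T3 falls shortly before delivery, eligibility requires a planned delivery at the study hospital, and the trial is double-masked with a placebo softgel, so strongly selective loss in one arm is an assumption without support in the text.

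A reader might also infer a large precision penalty from √(30/24) = 1.118, an interval about 12% wider. That compares completers with no loss at all. No analysis of the collected data recovers most of it; the recoverable part is the 1.4–3% above.

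Finally, a reader might want a carotenoid measurement when a woman leaves early. The schedule has none: "Mothers may be seen for Unscheduled Visits if deemed necessary for repeat measurements or follow-up of Adverse Events". Adding one means extra blood draws and imaging for leavers, and a reading between scheduled visits has no place in a T2/T3/Birth model. The fix does not need it.

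**Conclusion.** The mismatch between set and test is plain in the text and worth correcting. Its likely effect is modest. At most six women per arm are affected, planned power is about kept, and bias in the arm contrast is zero under completely random loss or equal selection in both arms. Under an assumed 20% selective loss in the supplemented arm alone it is about 5–7.5% of the 8,500-count difference, about 0.3 of a standard error. Other loss patterns reverse the sign, so neither direction nor size can be predicted. These figures rest on assumed correlations and dropout mechanisms, not on anything the documents report. The documents do not support reading this as an underpowered trial. The reason to act is that the declared efficacy set should be the set analysed, and a better method is available from data already scheduled.

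**What to change.** Make the primary maternal analysis a between-arm mixed model for repeated measures, one for each measure (serum, skin, macula), with T2, T3 and Birth as outcomes and baseline value, arm, visit and arm-by-visit as terms. Read the arm difference at Birth, which keeps the Section 1 time point. Every woman in the modified intent-to-treat set then contributes. Report the completers result as a sensitivity analysis.

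State also that women who stop the softgels are still asked to attend the scheduled visits, as Section 4, item 6 already does after a preterm delivery. This concerns attendance only. The sample-size text treats premature birth as a cause of later ineligibility, so those two passages should be reconciled at the same time.

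The cost is analysis-plan wording and slightly more programming, with no extra patients, visits or procedures. The gain is robustness to loss that depends on observed values, plus the small precision gain shown above. The downside is reliance on a missing-at-random assumption, which the data cannot confirm. The model can be fixed in the promised plan before database lock; the attendance sentence helps only women still under follow-up.

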Subgroup analyses will be performed to assess the influences of maternal dietary carotenoid intake, compliance with study supplement use, co-existing medical conditions, BMI, infant gender, and other factors on our study results, with proper attention to the effects of multiple tests on the ability to draw conclusions.

The complete statistical analysis plan will be finalized prior to database lock, and will provide statistical methods as well as descriptions of how missing, unused and spurious data will be addressed. Summarization of study data will be prepared of subject demographics, baseline characteristics, and investigational product exposure.

Safety Analyses

Serious and unexpected adverse events will be collected from the time of the first study supplement administration until a subject completes the study or discontinues prematurely. Treatment emergent adverse events (TEAEs) are defined as those AEs that develop or worsen after the first dose of study supplement and up to 30 days beyond the last dose of study medication. The current version of MedDRA will be used to classify all AEs.

Treatment- emergent adverse events will be summarized by System Organ Class and Preferred Term, in accordance with the MedDRA coding dictionary. The number of subjects reporting each AE preferred term will be tabulated for all TEAEs and separately for those considered as related to study treatment by the Principal Investigator. The number of subjects reporting SAEs will also be tabulated. Adverse event summaries will be presented for each treatment group separately.

Adverse events will be summarized by MedDRA coding terms, and separate tabulations also will be produced for related adverse events (those considered by the Investigator as definitively drug related), serious adverse events and discontinuations due to adverse events. Findings from ophthalmologic examinations will be tabulated for changes over time on study. Separate summaries will be prepared for systemic (non-ocular) and ocular AEs, with events in the study eye and non-study eye summarized separately.

Title: Lutein & Zeaxanthin in Pregnancy (L-ZIP) - Carotenoid Supplementation During Pregnancy: Ocular and Systemic Effects

Consent Process

1. The following investigators and internal staff will obtain consent (as indicated on the Study Location and Sponsors Page):

[name]	University of Utah
[name]	University of Utah
[name]	University of Utah
[name]	University of Utah

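### The maternal primary comparison uses only the T1-to-Birth change; adjusting for T1 as a covariate, preferably in a model that also uses T2 and T3, would be more precise at no extra data cost

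*Combined protocol and SAP*

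**What the plan says.** All references are to the combined protocol and SAP.

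- **Outcome.** Section 1, item 6 makes the primary outcome the change in serum, skin and macular carotenoids from enrollment to the final visit, which it identifies as the birth of the child.
- **Measurements.** The Study Visit Schedule (section 4, item 6) measures all three maternal tissues at T1 (before 14 weeks), T2 (22-26 weeks), T3 (37-39 weeks) and Birth. For the last of these, "All mothers will undergo a final assessment within two weeks of giving birth".
- **Test.** Efficacy Analyses (section 4, item 9): "Paired t-tests will compare the carotenoid status at enrollment and at the final study visit of the mothers" receiving supplementation and those not receiving it. Regression is named only for mother-infant associations. Diet, BMI and compliance appear only as subgroup factors.
- **Set.** "The primary, secondary and exploratory efficacy analyses will be performed using the modified Intent-to-Treat subject set". A randomized woman who receives product enters that set if she has "complete carotenoid evaluations for at least one trimester study visit while utilizing study supplements".
- **Deferral.** A complete SAP, due before database lock, "will provide statistical methods as well as descriptions of how missing, unused and spurious data will be addressed".
- **Planned loss.** The sample size section raises 20 per group to 30. Part of the allowance, about 20%, is "to plan for expected noncompliance and loss to follow up". For the outcomes other than skin it says "we estimate that a similar sample size of 20 patients per group will be sufficient to detect differences in these indices".

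**The concern.** A paired t-test compares two visits within the same women. To compare two independent arms, it has to become a comparison of the T1-to-Birth change. Three consequences follow.

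1. The change score fixes the baseline slope at 1. ANCOVA estimates the slope, which removes more of the between-woman variation unless the true slope is close to 1.
2. T2 and T3 are measured in every maternal tissue but enter no named efficacy test.
3. The set and the test do not match. A woman with T2 or T3 but no Birth value belongs to the modified Intent-to-Treat set yet cannot contribute a pair. The later SAP could supply a rule, but none is in the documents.

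The stake is precision, and women in the named set contributing nothing to the primary result. It matters most for the macula, where the plan gives no variance and only an expectation that 20 per group will be enough.

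**Working it through.** **Inputs from the plan (section 4, item 9, sample size).** Skin SD at birth 8300; difference 42,500 - 34,000 = 8,500 counts; 30 enrolled per arm; two-sided alpha 0.05; power 0.90.

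**Assumed, with ranges.** SD 8300 at every visit and in both arms; equal correlation ρ between visits, 0.3 to 0.9; 0 or 6 of 30 Birth values missing per arm. Six is the plan's 20%, which also covers noncompliance. The documents give no rate of missed Birth visits.

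**The plan's own figure.** n = 2 × (1.960 + 1.282)² × 8300² / 8500² = 20.04. Power at 20 per group is 0.8995, so the stated 20 reproduces. It is an unpaired comparison of Birth values. It matches a comparison of change only at ρ = 0.5, where the SD of change, 8300 × √(2(1-ρ)), equals 8300.

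**Formulas**, with m women per arm having a Birth value:
- Change: SE = √(4 × 8300² × (1-ρ)/m)
- ANCOVA of Birth on T1: SE = √(2 × 8300² × (1-ρ²)/m)
- Ratio of variances, ANCOVA to change: (1+ρ)/2
- Repeated-measures model: C is the covariance of T2, T3 and Birth given T1. V = inverse(m × C⁻¹ + k × J), where k women lack Birth and J is the inverse of the T2,T3 block of C padded with zeros. SE = √(2 × V₃₃).

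**None missing (m = 30).** The model and ANCOVA give the same SE.

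| ρ | Change | ANCOVA = model | Reduction |
|---|---|---|---|
| 0.3 | 2536 | 2044 | 19% |
| 0.5 | 2143 | 1856 | 13% |
| 0.7 | 1660 | 1530 | 8% |
| 0.8 | 1355 | 1286 | 5% |
| 0.9 | 958 | 934 | 2.5% |

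At ρ = 0.5 the gain equals raising 30 women per arm to 30 × 2/(1+0.5) = 40. At ρ = 0.9 it equals raising 30 to 32.

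**Six missing per arm, all with T2 and T3 (m = 24, k = 6).**

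| ρ | Change | ANCOVA | Model | Model vs change | T2/T3 add over ANCOVA |
|---|---|---|---|---|---|
| 0.3 | 2835 | 2286 | 2266 | 20% | 0.9% |
| 0.5 | 2396 | 2075 | 2040 | 15% | 1.7% |
| 0.7 | 1856 | 1711 | 1669 | 10% | 2.4% |
| 0.8 | 1515 | 1438 | 1398 | 8% | 2.8% |
| 0.9 | 1072 | 1044 | 1012 | 5.5% | 3.1% |

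If correlation is 0.8 or 0.9 between adjacent visits and decays with each further visit, change/ANCOVA/model are 2367/2058/1950 and 1764/1640/1540. T2/T3 then add 5-6%, or 2-3% if only T2 was seen. Simulating 20,000 trials per setting with the covariance estimated gives total reductions of about 14/9/6.5/4% at ρ = 0.5/0.7/0.8/0.9, slightly below the table.

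**Unequal SDs.** Set the Birth SD to 1 and the T1 SD to 1/r. The variance of change is 1/r² + 1 - 2ρ/r; the ANCOVA residual variance is 1 - ρ². At ρ = 0.8:
- r = 1.25: 0.64 + 1 - 1.28 = 0.36 against 0.36, so no gain.
- r = 0.8: 1.5625 + 1 - 2 = 0.5625 against 0.36, so the SE falls by 1 - √(0.36/0.5625) = 20%.

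**Skin power at 8,500 counts, change comparison**, Φ(8500/SE - 1.96):
- ρ = 0.5: 0.98 with none missing, 0.94 with six missing
- ρ = 0.3: 0.92 and 0.85

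**An outcome with 80% power under the change comparison**, Φ(2.80 × SE_change/SE_model - 1.96): 82-90% with none missing and 84-91% with six missing, for ρ from 0.9 down to 0.5.

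**The case against.** The strongest reply is that item 9 is a summary and the full methods and missing-data rules are deferred to a SAP not yet written. That stands as far as it goes. A reader might infer that the plan excludes women without a Birth value, but no such rule is written; their loss is only what a two-visit test does when nothing else is specified. The deferral does not answer the point, because the test and the set are already named and no method that uses the other visits is. The later SAP is where the change belongs.

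A reader might also infer that baseline is ignored. It is not: the change score subtracts it, and under randomization that comparison is unbiased. Only covariate adjustment is absent.

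It can fairly be said that the gain is small. T2 and T3 contribute nothing if all Birth values are present, and missed Birth visits may be few: the window opens at delivery, and women who deliver early are asked to complete it. For the macula, the plan describes the imaging as highly reproducible; if that means a correlation near 0.9, baseline adjustment gains only 2.5%. The equal-SD assumption also matters, since the plan gives an SD for skin only and at birth only. These points limit the size of the gain. They do not reverse it, because in large samples ANCOVA is never less precise than the change score.

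A reader might infer that the trial is underpowered for skin. The documents do not show that. With 30 enrolled per arm, power stays at 0.94 or more if correlation is at least 0.5, and falls to 0.85 only at 0.3 with six missing.

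**Conclusion.** The point holds as an improvement in efficiency. The named comparison leaves out information that the trial already plans to collect, mainly by not fitting T1 as a covariate. Under equal SDs and equal correlations, the Birth standard error falls by 2.5% to 19% for correlations from 0.9 down to 0.3, all of it from baseline adjustment when no Birth value is missing. T2 and T3 add about 1-3% with six of 30 missing per arm, or 5-6% if correlation decays between visits. With unequal SDs the gain from adjustment can be about zero or reach 20% or more. Correlation, missingness and SDs at visits other than Birth are assumptions throughout, and no figure is available for serum or macula. Nothing here shows that the planned comparison would reach a wrong conclusion, and no bias from missing Birth values has been demonstrated. Confidence in the size of the gain is medium.

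**What to change.** In the full SAP, make the primary analysis for each maternal tissue the between-arm difference at Birth adjusted for the T1 value.

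- **Preferred:** a likelihood-based repeated-measures model of T2, T3 and Birth with arm, visit, arm-by-visit, baseline and baseline-by-visit terms, unstructured within-woman covariance and Kenward-Roger degrees of freedom. Women without a Birth value then contribute through T2 and T3.
- **Minimum:** ANCOVA of the Birth value on T1. This gives most of the precision gain but still leaves those women out.
- **Report** by arm how many modified Intent-to-Treat women have no Birth value.
- **Optional:** the difference at 37-39 weeks, the last planned value in pregnancy, as a supportive result.

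The cost is SAP wording only; every measurement is already scheduled. The downsides are reliance on Birth values being missing at random given the earlier values and, if the optional contrast is used, one extra supportive comparison per tissue (three in all). Stating the between-arm estimate explicitly also removes the ambiguity of a paired test for two independent groups.
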